9.1.2 ANALYSIS FOR TIME TO EVENT DATA

The time to first event will be summarised in terms of mean, standard deviation, median, minimum and maximum. The table of the estimated hazard rate will be presented, along with a Kaplan-Meier plot of the hazard function.

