6.1. Endpoints

6.1.1. Primary Endpoint:

Impact of the following factors on the number of treatment escalations of Tofacitinib patients in 24 months

- a. DAS28-4 with Erythrocyte Sedimentation Rate (ESR)
- b. Δ DAS28-4 (ESR)
- c. Physician Global Assessment of Arthritis
- d. Patient's Assessment of Arthritis Pain
- e. Patient's satisfaction with drug treatment
- f. Patient's Global Assessment of Arthritis

Treatment escalation in this study is defined as a switch to another DMARD or combination of DMARDs when compared to the last visit.

6.1.2. Secondary Endpoints:

- a) Time to first treatment escalation
- b) Rate of Low Disease Activity (LDA) over time of patients on Tofacitinib (in combination therapy or monotherapy), as assessed by: Simplified Disease Activity Index (SDAI) \leq 11; Clinical Disease Activity Index (CDAI) \leq 10; DAS 28-4 (ESR) \leq 3.2 and DAS28-4 with C-reactive Protein (CRP) \leq 3.2.
- c) Rate of remission over time of patients on Tofacitinib (in combination therapy or monotherapy), as assessed by: American College of Rheumatology (ACR)-EULAR Boolean remission criteria; SDAI \leq 3.3; CDAI \leq 2.8; DAS 28-4 (ESR) $<$ 2.6 and DAS28-4 (CRP) $<$ 2.6
- d) Change from baseline over time of patients on Tofacitinib (in combination therapy or monotherapy) in DAS 28-4 (ESR) and DAS 28-4 (CRP)
- e) Change from baseline of duration of morning stiffness over time of patients on Tofacitinib (in combination therapy or monotherapy)

- f) Change from baseline in the Functional Ability Questionnaire Hannover (FFbH) over time of patients on Tofacitinib (in combination therapy or monotherapy)
- g) Rate of patients with functional remission in FFbH (FFbH > 83%) over time of patients on Tofacitinib (in combination therapy or monotherapy)
- h) Change from baseline in a self-report questionnaire (a quality of life instrument) developed by the European Quality of Life (EuroQoL) Group (EuroQoL EQ-5D) over time of patients on Tofacitinib (in combination therapy or monotherapy)
- i) Change from baseline in Functional Assessment of Chronic Illness Therapy (FACIT)-Fatigue scale over time of patients on Tofacitinib (in combination therapy or monotherapy)
- j) Drug survival at month 12, 24 of patients on Tofacitinib (in combination therapy or monotherapy)
- k) Patient's satisfaction with Tofacitinib treatment (in combination therapy or monotherapy) over time

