7.9.2.2. Secondary Analysis

7.9.2.2.1. Time to Event Analysis

Time to event endpoints will be investigated using Kaplan-Meier methodology and, where appropriate, Cox-Proportional Hazards modelling will be used to look at differences in event rate between sub-groups. The time to event will be summarised in terms of medians and confidence intervals. Kaplan-Meier plots of the time to event over the study duration will be presented.

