7.1.2.10 DRUG SURVIVAL STATUS OF TOFACITINIB

For patients who terminate tofacitinib, the drug survival status will be recorded as follows:

Those who terminate tofacitinib:

- Status = 1
- Time = Termination date tofacitinib – Date of initiation on tofacitinib

Tofacitinib is terminated when indicated on instrument “Rheumatologische Medikation” for therapy class tsDMARD/bDMARD variable *Change* (BDCM.CHANGECD) is set to “Therapy stop”. Tofacitinib pauses, where variable *Change* is set to “Therapy paused”, are not considered terminations.

Patients who do not terminate tofacitinib:

- Status = 0
- Time = Date of final visit – Date of initiation on tofacitinib

If patient is lost to follow-up or withdraws from the study they will be censored at the date of their last visit.

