9.2.3.1 TIME TO FIRST TREATMENT ESCALATION

Time to first treatment escalation will be analysed as in Section 9.1.2 using the SFAS. Missing or incomplete dates will not be imputed (as per Section 8.1).

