9.2.3.10 DRUG SURVIVAL STATUS OF TOFACITINIB

Time to cease taking tofacitinib (drug survival) will be analysed as per Section 9.1.2, using the SFAS. Missing data will not be imputed (as per Section 8.1).

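### SAP 9.1.2 summarises right-censored times by mean, SD, median, minimum and maximum without saying how censored times enter, and does not name the protocol's median with confidence interval or month-12 and month-24 drug survival

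*SAP*

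**What the plan says.** SAP 9.1.2 is the SAP's whole method for time-to-event data, in two sentences: "The time to first event will be summarised in terms of mean, standard deviation, median, minimum and maximum", then "The table of the estimated hazard rate will be presented, along with a Kaplan-Meier plot of the hazard function".

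Both time-to-event secondary endpoints are sent there. SAP 9.2.3.1: "Time to first treatment escalation will be analysed as in Section 9.1.2 using the SFAS". SAP 9.2.3.10: "Time to cease taking tofacitinib (drug survival) will be analysed as per Section 9.1.2, using the SFAS".

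The SAP defines both as censored data. Sections 7.1.2.1 and 7.1.2.10 set a 0/1 status and a time that ends at the event or the final visit. On drop-out, 7.1.2.10 says: "If patient is lost to follow-up or withdraws from the study they will be censored at the date of their last visit". Section 7.1.2.1 has the matching rule for escalation, and 8.1 repeats the principle. The summary table in 9.2.6 lists Kaplan-Meier plots and a table for both endpoints and refers back to 9.1.2.

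The protocol is more specific. Section 7.9.2.2.1: "Time to event endpoints will be investigated using Kaplan-Meier methodology" and "The time to event will be summarised in terms of medians and confidence intervals". Section 6.1.2, item j, defines the drug-survival endpoint at two time points: "Drug survival at month 12, 24 of patients on Tofacitinib (in combination therapy or monotherapy").

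**The concern.** Follow-up is 24 months per patient, so anyone still on tofacitinib or not yet escalated at that point is censored, as is anyone lost earlier. The five statistics in 9.1.2 are the ones that 9.1.3 lists for continuous data, which have no censoring. SD, minimum and maximum are not Kaplan-Meier quantities, so the natural reading is an ordinary descriptive table of recorded times.

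Such a table can be built in two ways, and 9.1.2 chooses neither. If all recorded times are used, a censored time counts as if the event had happened then. If only patients with an event are used, the table describes those who stopped or escalated within follow-up and says nothing about the rest. Two analysts following the text could report quite different persistence from the same data. The two quantities in the protocol that avoid the problem, a Kaplan-Meier median with its interval and drug survival at months 12 and 24, would not be required output.

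**Working it through.** **1. Passages side by side**

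| Item | Protocol | SAP |
|---|---|---|
| Method | Kaplan-Meier (7.9.2.2.1) | Kaplan-Meier plot and table (9.1.2, 9.2.6) |
| Location summary | Median with confidence interval (7.9.2.2.1) | Mean, SD, median, minimum, maximum; type of median and interval not stated (9.1.2) |
| Drug survival at months 12 and 24 | Named as the endpoint (6.1.2 j) | Not named in 7.1.2.10, 9.1.2, 9.2.3.10 or the 9.2.6 row |
| What the plot shows | Kaplan-Meier plot of time to event | Said to show the hazard function; a Kaplan-Meier plot shows the survival function |

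Protocol 7.9 lets the SAP modify protocol plans, but SAP section 2, which lists the changes, does not mention this one.

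**2. Size, by illustration**

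The plan states no figure to reproduce. The only input from the documents is the 24-month follow-up. Assumptions: exponential time to stopping; independent exponential loss of 30% by month 24; share still on drug at 24 months, S = 40% or 55%.

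Stopping rate λ = −ln(S)/24. Loss rate γ = −ln(0.70)/24 = 0.01486 per month. Let r = λ + γ and q = exp(−24r), the share still observed and event-free at month 24.

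- True median = ln 2/λ
- Restricted mean to 24 months = (1 − S)/λ
- Mean of all recorded times = (1 − q)/r
- Median of all recorded times = ln 2/r, if below 24
- Median among stoppers only = −ln[1 − (1 − q)/2]/r

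*S = 40%:* λ = 0.03818, r = 0.05304, q = 0.40 × 0.70 = 0.28.

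- True median = 0.6931/0.03818 = 18.2 months, inside follow-up
- Median of all times = 0.6931/0.05304 = 13.1 months
- Median among stoppers = −ln(0.64)/0.05304 = 8.4 months

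*S = 55%:* λ = 0.02491, r = 0.03977, q = 0.55 × 0.70 = 0.385.

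- True median = 0.6931/0.02491 = 27.8 months, beyond follow-up, so the Kaplan-Meier median would be reported as not reached
- Restricted mean = 0.45/0.02491 = 18.1 months
- Mean of all times = 0.615/0.03977 = 15.5 months, which is 2.6 months or about 14% lower
- Median among stoppers = −ln(0.6925)/0.03977 = 9.2 months
- Median of all times = 0.6931/0.03977 = 17.4 months, although fewer than half of patients truly stop within 24 months

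*No loss (γ = 0):* r = λ and q = S, so the mean of all times is (1 − S)/λ, exactly the restricted mean. It is still not the mean time to stopping, but it has a valid meaning. The distortion relative to the restricted mean comes from loss before month 24.

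**3. Does the Kaplan-Meier estimate avoid this?**

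In a separate simulation (200,000 exponential times, 50% event-free at 24 months, 20% loss), Kaplan-Meier gave survival of 0.71 at month 12 and 0.50 at month 24. These are the assumed values. The raw median of all times was 18.1 months against a true 24.0, and the events-only median was 9.4. With 30% event-free, the Kaplan-Meier median stayed at about 13.8 months at 0%, 20% and 40% loss, while the raw median fell from 13.7 to 11.6 to 9.7.

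**The case against.** A reader might infer from 9.1.2 that the SAP ignores censoring altogether. It does not. Sections 7.1.2.1, 7.1.2.10 and 8.1 define status and censoring, and 9.2.6 lists Kaplan-Meier plots and a table for both endpoints. The gap is confined to how the listed statistics are computed.

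A reader might also infer that the protocol's median and interval were replaced. A median is still listed and may be meant as the Kaplan-Meier median, and SAP section 5 promises appropriate confidence intervals in tables generally. The interval is unspecified for these endpoints, not removed. Month-12 and month-24 survival could be read from a Kaplan-Meier table, and the table shells, kept in a separate document under section 10, may name them. Those two time points belong to drug survival only, not to time to first escalation.

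Nor should raw summaries be scored against true medians beyond 24 months, such as 27.8 here. No analysis of 24-month data can estimate those without extrapolation, and the fix would not recover them. Loss may also be lower than assumed: protocol 7.12 expects follow-up after switching to keep more patients in the study.

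All of this stands and narrows the point. It does not remove it. The 9.2.6 entry refers back to 9.1.2, which names no survival estimate, and no reading makes an SD or maximum of censored times a proper summary of time to event.

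**Conclusion.** Wrong as written for the mean and SD, and unspecified for the median, its interval and the month-12 and month-24 drug survival. Under the assumed exponential stopping and 30% loss, the median of all recorded times is about 5 months too low when 40% remain on drug (13.1 against 18.2). The mean of all times is about 2.6 months below the restricted mean when 55% remain (15.5 against 18.1), and a stoppers-only median is about 9 months where the true median is not reached within follow-up. These sizes depend on stopping and loss rates that the documents do not give, and no separate calculation was made for time to first escalation. With no loss, the mean of all times equals the restricted mean.

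Both endpoints are secondary and descriptive, with no decision rule attached. The primary recurrent-event analysis and the sample size are unaffected.

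**What to change.** Rewrite SAP 9.1.2 to require:

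- for both endpoints, the Kaplan-Meier median with 95% CI, reported as not reached where that applies;
- for drug survival, Kaplan-Meier estimates at months 12 and 24 with 95% CI, also named in 7.1.2.10 and 9.2.3.10;
- the numbers of events and of censored patients;
- no raw mean or SD; if a mean is wanted, the restricted mean to 24 months;
- the plot labelled as the survival function.

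The cost is a few lines of SAP text and matching table shells. The estimates are standard survival-procedure output from data already collected.

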9.1.3 ANALYSIS OF CONTINUOUS DATA

The absolute values and change from baseline in each endpoint will be summarised for each time point using N, mean, standard deviation, median, minimum and maximum.

9.1.4 ANALYSIS FOR BINARY DATA

Binary data will be presented using counts and percentages. To calculate the percentage, the denominator will be the number of subjects with a non-missing value. These will be presented for each time point.

9.1.5 ANALYSIS OF CATEGORICAL DATA

Categorical data will be summarized in terms of number and percentage of patients within each category at each visit. Shift tables of changes from baseline will also be presented.

9.1.6 COMPARISON BETWEEN TREATMENTS

As there is only one cohort, those who are initiated on tofacitinib, there will be no formal comparison between treatment groups, although endpoints may be summarised by treatment subgroups (Section 6.6). All descriptive statistics will be presented overall and for all secondary analyses this will only be done using the data recorded when patients were taking tofacitinib.

9.2 STATISTICAL ANALYSES

The statistical software SAS 9.3 (or higher) will be used to conduct the statistical analysis.

The results will be presented in tables and plots programmed within SAS.

Both the interim and final analyses will be performed using the methods described in this SAP. The outputs to be produced for the interim analysis will be flagged in the list of tables.

9.2.1 BACKGROUND AND DEMOGRAPHIC CHARACTERISTICS AND STUDY DISPOSITION

The Demographic and baseline variables will be summarised:

Continuous: Mean, standard deviation, median, minimum and maximum

Categorical: Frequency and Percentage of population.

This will include age, sex, height, weight, smoking history, smoking status, severity of disease, duration of disease, anti-citrullinated protein antibodies (ACPA) / RF, vaccination status, presence of Poor Prognostic Factors, comorbidities, co-medication and concomitant medication and will be based on the Full Analysis Set.

The number and percentage of patients at each time point will be provided along with reasons for withdrawal from the study. For patients who have discontinued tofacitinib treatment but remain in the study, information on the treatments prescribed following study treatment (tofacitinib) will be provided.

The baseline visit for each patient will be their Baseline (Enrollment) visit (Visit 1).

9.2.2 PRIMARY ANALYSES

Each of the factors that will be included in the models for the primary analysis will be summarized by time point.

The Primary endpoint will be analysed as recurrent event data (as described in Section 9.1.1). The factors of interest as well as potential confounders (as described in Section 7.3.1 and section 6.3.3 respectively) will be included so as to determine whether they have an impact on the rate of treatment change. The population used for this analysis will be the FAS, including all visits (scheduled and unscheduled). The analysis will be repeated using the PPAS with visit windows as outlined in Section 12.1.1).

Escalations occurring in-between two planned visits will be assigned to visits using the visit windows provided in section 12.1.1. If two or more escalations fall into the same window, all escalations will be counted. Escalations, which are assigned to the baseline visit, will be counted under the Month 3 Visit, unless the escalation occurred before first tofacitinib treatment. Escalations, which fall outside the visit windows, will be assigned to the visit nearest to the Target Day. If two visits are equal distance from the escalation date in absolute value, the later visit should be used.

Sensitivity analyses, using both the FAS and PPAS, will be carried out with the covariates mentioned in section 7.3 along with the confounders mentioned above. An exploration of covariates will be carried out to assess any collinearity.

A further sensitivity analysis will be carried out using the FAS and PPAS population where treatment switches will be assigned to the visit prior to the date at which it occurred.

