7.1.2.4 CHANGE FROM BASELINE IN DAS28-4 (ESR) AND DAS28-4 (CRP)

7.1.2.4.1 DAS28-4

$\text{DAS28-4 (ESR)} = 0.56*\sqrt{(\text{TJC28})} + 0.28*\sqrt{(\text{SJC28})} + 0.70*\ln(\text{ESR in mm/ hour}) + 0.014*\text{PtGA in mm.}$

DAS28-4 (CRP) is similarly calculated by:

$\text{DAS28-4 (CRP)} = 0.56*\sqrt{(\text{TJC28})} + 0.28*\sqrt{(\text{SJC28})} + 0.36*\ln(\text{CRP in mg/l} + 1) + 0.014*\text{PtGA in mm} + 0.96$

Where TJC28 is the Tender Joint Count, SJC28 is the Swollen Joint Count, CRP is the C-reactive protein in mg/L, ESR is the Erythrocyte Sedimentation Rate in mm/first hour and

PtGA is the Patient's Global Assessment of Health in mm. PtGA will be used in this calculation.

The change from baseline in DAS28-4 (ESR) will be calculated at each time point as:

DAS28-4 (ESR) at time point – DAS28-4 (ESR) at baseline.

Similarly change from baseline in DAS28-4 (CRP) will be calculated at each time point as:

DAS28-4 (CRP) at time point – DAS28-4 (CRP) at baseline.

Change from Baseline in DAS 28-4 at all time points (M3, M6, M9, M12, M15, M18, M21, M24) will be presented.

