8 HANDLING OF MISSING VALUES

8.1 TIME TO EVENT (PRIMARY ANALYSIS, TIME TO FIRST TREATMENT ESCALATION AND DRUG SURVIVAL)

Time to event should be determined for the events without any date imputation.

If a patient experiences the event of interest the status will be 1, and the time will be the time at which the event occurred (or visit at which it was recorded).

If a patient doesn't experience the event of interest the status will be 0, and the time will be the last time that the patient was known to be in the study (last visit). If this is not the end of the study then the time will be censored at this time point.

The primary endpoint is a time-to-event endpoint, although it takes into account the possibility of multiple events occurring for each patient. For each patient the data for analysis should consist of the times at which they experienced the event of interest and the values of the covariates at each time point. Any missing data within the covariates to be included in the models for primary analysis will be replaced by the nearest available value to the event. If more than one value qualifies, the later value will be used .

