9.1.1 ANALYSIS FOR RECURRENT EVENT DATA

In order to account for the possibility that there are multiple events occurring for each patient cox-proportional hazards modeling will be used with adjustment for recurrent events. This involves fitting either the Andersen and Gill or Prentice, Williams and Peterson gap-time models to the data.

For each patient, the data will be split into time periods, then data for each time window should include the patient's status, the time of event (if the event occurred) and the value of each of the factors of interest:

So, for patient A, who had events at M6 and M18, their data could look like this:

Patient	Start	Stop	Treatment Escalation Status	Factor A	Factor B	Factor C
A	0	M6	1	3.9	0.6	-10
A	M6	M12	0	3.0	1.5	-20
A	M12	M8	1	2.8	1.7	-10
A	M18	M24	0	2.2	2.3	-10

The cox proportional hazards model (using PROC PHREG) is then used, including the factors of interest (Section 7.3.1) to determine which, if any of them, have an impact on the rate at which treatment changes occur.

Any potential confounders should be included in the model also (Section 7.3.3).

The estimated event rate will be presented, along with 95% confidence interval and p-value, for each of the covariates of interest. Note: These will not be presented for the variables considered to be confounders.

The number and proportion of people experiencing an event at each time point will be presented.

Supportive tables will also be presented which summarises each of the covariates in the model at each visit.

The analysis will be performed for each type of escalation as defined in section 7.1.1 and overall.

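### The primary model has no rule that covariates be measured on or before the escalation, so values recorded after a switch can be used as predictors of it

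*SAP*

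**What the plan says.** The objective (Protocol 6, SAP 3.3) is to identify the factors behind rheumatologists' treatment decisions. The primary analysis (SAP 9.1.1, 9.2.2) is a recurrent-event Cox model in the FAS with six factors updated over time. The rules that bear on timing are these.

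- **Event time (SAP 8.1).** "Time to event should be determined for the events without any date imputation". For a patient with an event, "the time will be the time at which the event occurred (or visit at which it was recorded").
- **Covariates.** SAP 8.1 describes each patient's data as "the times at which they experienced the event of interest and the values of the covariates at each time point". SAP 9.1.1 asks each time window to hold "the time of event (if the event occurred) and the value of each of the factors of interest". Neither names the visit that supplies the value.
- **Missing covariates (SAP 8.1).** They are "replaced by the nearest available value to the event. If more than one value qualifies, the later value will be used". The summary table in SAP 9.2.6 lists imputation for the primary FAS model.
- **Escalations between visits (SAP 9.2.2, repeated in 12.1.1 for the primary endpoint).** They go to the visit whose window contains them, otherwise to the nearest visit, with ties to the later one. In addition, "Escalations, which are assigned to the baseline visit, will be counted under the Month 3 Visit". The only exception is an escalation before the first tofacitinib treatment.

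A further sensitivity analysis assigns each switch to the visit before it, in both the FAS and the PPAS.

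**The concern.** A value recorded after a switch partly reflects the new treatment. The satisfaction item shows this plainly: it asks about the drugs received since the last visit, so an answer given after a switch can partly rate the new drug. If such values enter the model as predictors, the estimate mixes what led to the switch with what followed it.

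The bias has no fixed direction. If scores improve after step-ups, a true association is attenuated or reversed. If they worsen after terminations or step-downs, which SAP 7.1.1 also counts as escalations, it is inflated. The results at stake are the primary ones: the hazard ratios for the six factors.

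**Working it through.** **1. Two readings of the text.** On the *assigned* reading, the visit to which the escalation is assigned supplies the covariates. On the *nearest* reading, the value at or nearest the event time is used, and visit assignment serves only the by-visit counts.

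The example table in SAP 9.1.1 ("So, for patient A, who had events at M6 and M18, their data could look like this") gives only a hint. Factor A + Factor B is 3.9 + 0.6, 3.0 + 1.5, 2.8 + 1.7 and 2.2 + 2.3, which is 4.5 in every row. That would fit a DAS28 level and its improvement, both read at the end of the interval. But the factors are unnamed, and improvement would have to be coded as positive. SAP 7.1.2.4.1 ("The change from baseline in DAS28-4 (ESR) will be calculated at each time point as") takes time point minus baseline, the opposite sign.

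**2. Windows.** Target day ±14 (Month 3) or ±28 (later visits) reproduces Table 11.1: 91 ± 14 = 77 to 105, 182 ± 28 = 154 to 210, and so on to 730 ± 28 = 702 to 758.

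**3. Days mapped to a later visit, with visits on target days.** Every midpoint between target days after Month 3 falls in a gap between windows, so the window rule and the nearest-visit rule agree there. Where the table rule speaks of nearness to the target day, I read it as nearness to the escalation date, as its tie rule does.

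| Between target days | Assigned: days mapped later | Nearest: days mapped later |
|---|---|---|
| 1 and 91 | 2–90: 89 | 46–90: 45 |
| 91 and 182 | 137–181: 45 | 45 |
| 182 and 273 | 228–272: 45 | 45 |
| 273 and 365 | 319–364: 46 (tie at 319) | 46 |
| 365 and 456 | 411–455: 45 | 45 |
| 456 and 547 | 502–546: 45 | 45 |
| 547 and 638 | 593–637: 45 | 45 |
| 638 and 730 | 684–729: 46 (tie at 684) | 46 |
| Total of 728 | 406 (56%) | 362 (50%) |

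On the assigned reading, 7 further days coincide with a visit and 315 map to an earlier one. On 75 + 17 + 17 + 18 + 17 + 17 + 17 + 18 = 196 days (27%) the whole assigned window lies after the switch.

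**4. Visits off schedule.** Visits 2 to 9 were each shifted uniformly within ±14, ±28 or ±42 days (2000 replicates). The assigned reading gives 55/55/55% overall and 96/92/89% on days 2–90. The nearest reading gives 49/49/48% and 46/42/39%.

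**5. Switches soon after visits.** Suppose every switch falls 1 to 45 days after one of visits 1 to 8, giving 8 × 45 = 360 possible days. The assigned reading then uses a later visit on 45 (12.5%), all in the first interval. The nearest reading does so on 1 (0.3%, the tie at day 46). If switches fall on visit days and values are present, there is no effect after baseline.

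**6. Direction of bias.** Simulation of 1500 patients × 8 intervals, with 3.16/8 events per interval, a Cox model stratified by interval, one factor at a time, and 100 replicates per cell. The coefficient is 0.01 per mm (the size in Protocol 7.7, with a worse score taken to mean more escalation), so the true HR per 10 mm is exp(0.1) = 1.105. The spread is the Protocol 7.7 SD of change (pain 24.672). The shift after the switch and the share of events using a post-switch value are assumptions.

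| Pain after switch | 12.5% | 27% | 50% | 56% |
|---|---|---|---|---|
| 20 mm better | 1.07 | 1.03 | 0.97 | 0.95 |
| 10 mm better | 1.09 | 1.07 | 1.03 | 1.02 |
| 10 mm worse | 1.12 | 1.14 | 1.18 | 1.18 |
| 20 mm worse | 1.14 | 1.18 | 1.24 | 1.25 |

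A zero shift returns 1.10 to 1.11. At 56%, going from 20 mm better to 20 mm worse, the physician global runs from 1.00 to 1.20 and the patient global from 1.04 to 1.16.

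A separate simulation took low disease activity as the factor, a DAS28 fall of 0.5 to 1.0 after a switch, and 0 to 80% of switches on visit days. With a true HR of 1.00, the assigned reading gave 1.13 to 1.93 and the value before the switch gave 0.97 to 1.01.

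**The case against.** The strongest reply is that the visit assignment may not govern covariates at all. Its wording is about counting, SAP 8.1 sets event time by occurrence, and a start–stop dataset can carry the value from the start of each interval. On that reading, post-switch values enter only through imputation. The 50% figure also treats every between-visit event as lacking a value, although the imputation rule applies only to missing covariates and the documents give no missingness rate. The FAS includes unscheduled visits, which the day counts leave out; a switch decided at such a visit may have same-day values. Days are not events, and where switches follow visits closely the effect is small. Finally, the plan already includes prior-visit analyses.

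Much of this limits the size, and it stands there. It does not remove the gap. SAP 12.1.1 ties the assignment to the primary endpoint analysis. The start-of-interval reading is not stated and sits poorly with SAP 8.1, and it would still allow imputation from later values. Protocol 7.8 expects missing values, so that rule will be used. Of the prior-visit runs, the FAS version still lists imputation in SAP 9.2.6. The PPAS version lists none and so removes both routes, but it keeps only scheduled visits inside their windows, and SAP 2 expects many visits outside the protocol's windows. Neither run is primary.

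**Conclusion.** The concern holds. No rule in the primary FAS model requires a covariate to be measured on or before the escalation, and both the assigned and the nearest reading allow post-switch values. That the text is silent is certain. The size of the consequence is not known from the documents.

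The share of possible switch days affected runs from none or almost none (switches at or soon after visits, nearest reading) to 56% (switches spread evenly over time, assigned reading). With assumed changes of 20 mm in either direction, a true pain HR of 1.105 per 10 mm becomes 1.07 to 1.14 at a 12.5% share and 0.95 to 1.25 at 56%. These figures show direction and possible scale. They are not a forecast, because the SAP model has six factors plus confounders and is fitted as Andersen–Gill or gap-time. The point should be fixed, since the order of predictor and decision is the core of the research question.

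**What to change.** **SAP 9.1.1 and 9.2.2**
- Use the recorded escalation date as event time in the primary model. For each escalation type, state which recorded date defines it: stop of the previous DMARD or start of the new one (for a replacement, for example, the earlier of the two).
- Use the visit of recording only if the date is missing, and then take covariates from before that visit, because the switch may have preceded it.
- Take each covariate from the last scheduled or unscheduled assessment on or before the escalation date, including the day of the decision. Say so in words beside the example table.
- Keep the window and nearest-visit assignment as a sensitivity analysis.
- Report the number of first-interval escalations and fit the model with and without them. At baseline the DAS28 change is zero by definition, and satisfaction refers to prior treatment (Protocol 7.5.1.1).

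**SAP 8.1**
- Impute only from earlier values, by one rule for intervals with and without an event. At present there is no rule for intervals without one.

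**Cost.** SAP wording and programming of the analysis dataset. No new data are needed, since Protocol 7.6.5 already collects stop and start dates. The price is that some covariates will be up to about three months old and may miss a flare that prompted the switch. First-interval escalations will also carry little information on DAS28 change and satisfaction.
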